12.1. Adverse Events

AEs will be coded according to the MedDRA Version 21.0. Unless otherwise specified, AEs will be summarized by SOC and PT, with SOCs presented in the standard international order and PTs within each SOC in descending order of subject incidence.

A subject data listing of all AEs (including TEAEs and non-TEAEs) will be provided.

12.1.1. Overall Summary of Adverse Events

An overall summary of the following AE categories will be provided:

- Any TEAE
- Any drug-related TEAE
- Any severe TEAE
- Any serious TEAE
- Any serious drug-related TEAE
- Any TEAE leading to drug interruption
- Any TEAE leading to drug withdrawal
- Any TEAE leading to death

12.1.2. All TEAEs

Summarization of all TEAEs by the following categories will be provided as appropriate:

- Any TEAEs (by SOC and PT, and by PT only)
- Any TEAEs by exposure interval (≤ 1 , > 1 to ≤ 4 , > 4 to ≤ 12 , > 12)
- Any TEAEs by age category (< 65 , ≥ 65 years) and gender
- Any TEAEs by prior methotrexate use (Yes/No)
- Any TEAE by concomitant methotrexate use (Yes/No)

For the summary of any TEAEs by exposure interval, the AE data will be handled per the following rules, unless otherwise specified.

- An event with a start date falling into an exposure interval is considered a new event for that interval.
- Each subject is counted once for either subject incidence or EAIR for each applicable specific TEAE in each exposure interval where an event started.
- The denominator of a subject incidence is the number of subjects with treatment duration exceeding the lower bound of the particular exposure interval, while the denominator of an EAIR is the sum of the exposure time during the exposure interval (up to the first event start date for subjects with at least one event starting in the interval) among the same number of subjects as in the denominator of the corresponding subject incidence.

Summarization of the TEAEs with the following specifications will be provided as appropriate:

- Most frequent TEAEs ($\geq 5\%$; by SOC and PT, and by PT only in descending order of subject incidence)
- Most frequent TEAEs by onset interval and event duration (for special interest of PTs: Diarrhoea, Headache, Nasopharyngitis, Nausea, Hypertension, and Upper respiratory tract infection)
- Any drug-related TEAEs (by SOC and PT)
- Any drug-related TEAEs by exposure interval (refer to Section [12.1.2](#))
- Any serious TEAEs (by SOC and PT)
- Any serious TEAEs by exposure interval (refer to Section [12.1.2](#))
- Any serious TEAEs by age category ($<65, \geq 65$ years) and gender
- Any serious drug-related TEAEs (by SOC and PT)
- Any serious drug-related TEAEs by exposure interval (refer to Section [12.1.2](#))
- TEAEs by maximum severity (by SOC and PT)
- Any TEAEs leading to study drug withdrawal (by SOC and PT)
- Any TEAEs leading to study drug withdrawal by age category ($<65, \geq 65$ years) and gender
- Any TEAEs leading to study drug withdrawal by prior use of psoriatic arthritis medications
- Any TEAE leading to study drug withdrawal by concomitant use of psoriatic arthritis medications
- Any TEAEs leading to study drug interruption (by SOC and PT)
- Any TEAEs leading to death (by SOC and PT)

For drug-related TEAEs, the relationship of an AE to IP is recorded on the Adverse Events - Serious Adverse Events eCRF page as “NOT SUSPECTED” and “SUSPECTED”. Adverse events with missing relationship to IP will be assessed as drug-related.

For TEAEs by maximum severity, if a subject reports multiple occurrence of a specific event within a specific analysis period, the subject will be counted only once by the maximum severity (mild, moderate, severe, or, if needed, missing). If a subject reports multiple TEAEs within an SOC, the subject will be counted only once for that SOC at the maximum severity. If the severity

is missing for one or more of the occurrences/TEAEs, the maximum severity of the remaining occurrences will be used. If the severity is missing for all the occurrences/TEAEs, the subject will be counted only once in the “missing” category of severity.

In addition, subject data listings for serious AEs (both TEAEs and non-TEAEs), TEAEs leading to drug withdrawal, and deaths will be provided.

12.2. Adverse Events of Special Interest

Adverse events of special interest (AESI) include diarrhea.

Protocol defined diarrhea AEs, referring to events with 2 or more watery or liquid stools in a day, will be captured on the site pad by ERT. Duration and frequency of the individual diarrhea will be captured. The diarrheas reported on the site pad will need to be reconciled with the events captured on Medidata’s RaveX EDC platform.

Frequencies (Daily, 5 – 6 days per week, 2 – 4 days per week, once every other week to once a week) of these events will be summarized.

A listing of AESIs will be also provided.

12.3. Clinical Laboratory Evaluations

Clinical laboratory evaluations will be available from the central laboratory and include:

- Hematology: complete blood count (CBC) (red blood cell [RBC] count, hemoglobin, hematocrit, white blood cell [WBC] count and differential, absolute WBC counts, platelet count).
- Serum chemistries: total protein, albumin, calcium, phosphorous, glucose, triglycerides, total cholesterol [TC], total and direct bilirubin, alkaline phosphatase, AST, ALT], sodium, potassium, chloride, bicarbonate [carbon dioxide, CO₂], blood urea nitrogen [BUN], creatinine, lactate dehydrogenase [LDH], and magnesium.
- Urinalysis: specific gravity, pH, glucose, ketones, protein, blood, bilirubin, leukocyte esterase, nitrite, and urobilinogen; if urinalysis is abnormal, microscopic urinalysis (epithelial cells, RBC, WBC, and casts) will be performed.

Summary statistics of observed values and changes from baseline in hematology and serum chemistry parameters will be provided over time. Frequency summaries (shift tables) of shifts from baseline to post-baseline time points and to the worst post-baseline value, in terms of low/normal/high/both low and high, will be provided for hematology and serum chemistry parameters. Subject data listings of all laboratory data, including urinalysis, will be provided.

Summary of the categories of laboratory marked abnormalities will be provided based on the marked abnormalities criteria. Subject incidence and EAIR for each abnormality will be calculated based on subjects with a baseline value and at least one post-baseline value for criteria

requiring baseline or subjects with at least one post-baseline value for criteria not requiring baseline.

A separate summary of laboratory marked abnormalities will also be presented by categories of subjects with normal values at baseline and subjects with abnormal values at baseline. To the purpose of these summaries, subjects with abnormal (normal) values at baseline are defined as those whose baseline value is low (not low) for criteria concerning low values and those whose baseline value is high (not high) for criteria concerning high values; both low and high are relative to the laboratory normal range.

A subject data listing of laboratory marked abnormalities will be provided. In the listing, all recordings of a lab analyte will be displayed for the subject if that subject has one or more marked abnormalities for the test.

For comorbid conditions of interest or a subgroup of subjects, summary statistics of relevant laboratory parameters over time may be provided. A subject listing will be also provided for all available pregnancy test results.

12.4. Vital Sign Measurements and Weight

For vital signs and weight, summary statistics (n, mean, standard deviation, median, minimum, the 25th (Q1) and 75th (Q3) percentiles, maximum, percent change from baseline for weight only) of observed and change from baseline values will be presented.

For vital signs (excluding weight), Frequency summaries (shift tables) of shifts from baseline to post-baseline or worst post-baseline values (low/normal/high/both low and high) during the treatment in below, within and above the normal ranges will be displayed in cross-tabulations.

For weight, change and percent change from baseline to the end of the study will be presented, as well as by baseline BMI and baseline weight categories.

12.5. Physical Examination

Physical examination findings will be captured as medical history (screening) or abnormal physical examination findings will be reported as adverse events and will be reported in those summaries.

12.6. Concomitant Medications/Procedures

Concomitant medications and procedures will be summarized for the safety population. Subject data listings for concomitant medications and procedures will be also provided.

12.6.1. Concomitant Medications

Concomitant medications are defined as medications that administered on or after the first dose of the IP or those started prior to the first dose of the IP but stopped on or after the date of the first dose of IP, or recorded as ongoing. The Anatomical Therapeutical Chemical (ATC) coding scheme of the World Health Organization Drug Dictionary (WHODD; Version March 2018) will

be used to group medications into relevant categories. A frequency summary of concomitant medications will be provided by ATC2 level and standardized medication name.

12.6.2. Concomitant Procedures

Concomitant procedures are defined as procedures that were done on or after the first dose of the IP or those started prior to the first dose of the IP but stopped on or after the date of the first dose of IP, or recorded as ongoing. Concomitant procedures will be coded according to MedDRA Version 21.0. A frequency summary of concomitant procedures will be provided by SOC and preferred term.

APPENDIX A1

Following are the general conventions for various computations and imputations for references. Users may need to consult with study team for specific study practices or regulatory guidelines.

1. Guideline of Partially Missing Date Imputation

1.1 Adverse Events

The principle of the imputation rules for subjects who were treated with apremilast initially is to treat the AE as treatment-emergent, i.e., occurring on or after the date of the first dose of IP, if possible.

Partially missing AE start date will be imputed in the ADaM dataset for AEs, but partially missing AE end dates will not be imputed in the same dataset. If the AE end date is complete with no missing year, month, or day, and the partially missing start date imputed by the rules below is after the AE end date, then the start date will be imputed by the AE end date.

The following scenarios are considered in the imputation rules:

- If AE start day is missing, and AE start month and year are not missing:
 - If AE start year and month are the same as the year and month of first dose, then impute AE start day using the day of first dose date.
 - If AE start date is less than the first dose date, then impute AE start day using the last day of AE start month.
 - If AE start date is greater than the first dose date, then impute AE start day using the first day of AE start month.
- If both AE start month and day are missing, and AE start year is not missing:
 - If AE start year is less than the year of first dose, then impute AE start date using the last day of the AE start year.
 - If AE start year is equal to the year of first dose, then impute AE start date using the first dose date.
 - If AE start year is greater than the year of first dose, then impute AE start date using the first day of the AE start year.

1.2 Prior/Concomitant Medications and Procedures

Partially missing start/stop dates for prior/concomitant medications and partially missing start dates for prior/concomitant procedures will be imputed in the ADaM dataset for prior/concomitant medications/procedures.

For prior/concomitant medications, if the stop date is complete with no missing year, month, or day, and the partially missing start date imputed by the rule below is after the stop date, then the start date will be imputed by the stop date.

Partially missing prior/concomitant medication/procedure start dates will be imputed by the earliest possible date given the non-missing field(s) of the date.

Partially missing prior/concomitant medication stop dates will be imputed by the latest possible date given the non-missing field(s) of the date.

1.3 Medical History

Partially missing medical history start dates will be imputed in the ADaM dataset for medical history (for the purposes of calculating durations of PsA and psoriasis). The 16th of the month will be used to impute a partially missing start date that has only the day missing, and July 1st will be used to impute a partially missing start date that has both the month and day missing.

1.4 Treatment Duration

Partially or completely missing last dose dates will be imputed in the ADaM dataset for treatment duration. When partially missing last dose date is available, set last dose date to the maximum of [the earliest possible date given the non-missing field(s) of last dose date, the minimum of (the latest possible date given the non-missing field(s) of last dose date, last known date in database, first non-missing Early Termination (ET) visit date)] When last dose date is completely missing, set last dose date to the minimum of (last known date in database, first non-missing Early Termination (ET) visit date) Last known date in database is defined as maximum of (last visit date, lab, vital signs, AE start or end dates, concomitant medications start or end dates, concomitant procedure date, last dose date from 'Disposition- Treatment' page, treatment exposure start date or end date where doses were completely or partially taken, death date).

2. Marked Abnormalities Criteria

Table 8: Marked Abnormalities Criteria

Category / Analyte	SI Units	Criteria
Chemistry/ ALT/AST	U/L	3*ULN
Alanine Aminotransferase (SGPT)	U/L	3*ULN
Albumin	kg/m ³	<25
Alkaline Phosphatase	U/L	> 400
Aspartate Aminotransferase (SGOT)	U/L	3*ULN
Bilirubin	µmol/L	> 1.8xULN
Bilirubin and ALT/AST	umol/L U/L	(ALT or AST > 3xULN) and bilirubin > 2xULN
Blood Urea Nitrogen	mmol/L	>15
Calcium	mmol/L	1. < 1.8 2. > 3.0
Cholesterol	mmol/L	> 7.8
Creatinine	µmol/L	> 1.7*ULN
Glucose	mmol/L	1. < 2.8 2. > 13.9
Lactate Dehydrogenase	U/L	> 3*ULN
Magnesium	mmol/L	> 1.2
Phosphate	mmol/L	1. < 0.64 2. > 1.6
Potassium	mmol/L	1. < 3.0 2. > 5.5
Sodium	mmol/L	1. < 130 2. > 150
Urate	umol/L	Male: > 590; Female: > 480
Hematology/ Basophils	10 ⁹ /L	> 3
Eosinophils	10 ⁹ /L	1. > 0.8 2. Increase \geq 100% and value > 0.8

Category / Analyte	SI Units	Criteria
Hematocrit	Ratio	1. < 0.27 2. Male: > 0.55; Female: > 0.50
Hemoglobin	g/dL	1. Male: < 10.5 or Female < 8.5 2. Male: > 18.5 or Female > 17
Hemoglobin A1C	%	> 9
Leukocytes	10 ⁹ /L	< 1.5
Lymphocytes	10 ⁹ /L	< 0.8
Neutrophils	10 ⁹ /L	< 1
Platelets	10 ⁹ /L	1. < 75 2. > 600

ULN = upper limit of normal

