### **3.3. End of Trial**

The End of Trial is defined as either the date of the last visit of the last subject to complete the post-treatment follow-up, or the date of receipt of the last data point from the last subject that is required for primary, secondary and/or exploratory analysis, as prespecified in the protocol, whichever is the later date.

Study completion is defined as the date of the last visit of the last subject in this clinical study. Study completion for an individual subject is defined as reaching Visit 7/48 weeks of treatment, and finishing the Observational Follow-up Visit at Week 52. A subject not meeting this definition is considered under early discontinuation (see Section 6.3). For the purpose of analyses, study completion for an individual subject is defined as reaching the Week 48 Visit.

Approved

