#### 6.2.1. End of Treatment/Early Termination Visit

An Early Termination Visit will be performed for subjects who are withdrawn from treatment for any reason, as soon as possible, after the decision to permanently discontinue treatment has been made.

The following will be performed as specified in the Table of Events:

- Complete physical examination (source documented only), weight
- Vital signs
- Concomitant medications evaluation
- Concomitant procedures evaluation
- Subject-reported outcomes
- Adverse event/Serious Adverse Event evaluation/assessment
- Assessment of diarrhea
- Hematology panel including complete blood count (CBC) with differential and platelet
- Chemistry panel
- Hemoglobin A1c
- 
- Urinalysis
- Serum  $\beta$ -hCG (for FCBP subjects)
- Efficacy assessments, including MRI
- IP accountability

Approved

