5.3. Analysis Periods

In this study, the analysis periods are divided into open label treatment period and observational follow-up period below.

- Open label treatment period – Week 0 to Week 48

This period starts on the day after the first IP is dispensed (Visit 2/Week 0), and stops on either: (1) the completion date of treatment period collected in the eCRF; or (2) the early termination date of treatment period collected in the eCRF; or (3) the last known study date if the subject is lost to follow-up.

- Observational follow-up period – 4 weeks

Subjects who complete the study or early terminate from the study, will be followed up for 28 days after the Visit 7/Week 48 or Early Termination visit. The period starts at the end date of treatment period + 1 and stops on either (1) the completion date of follow-up period in eCRF; (2) the last known study date if the subject is lost to follow-up.

For efficacy analysis, only the open-label treatment period will be used.

For safety analysis, the open-label treatment period and observational follow-up period will be included into the data summary.

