10.1. Treatment Duration

Summary statistics for treatment duration (in weeks), as well as a frequency summary of treatment duration categories (e.g., < 8 weeks, \geq 8 to < 16 weeks, etc.) will be summarized for FAS and safety population. A subject data listing of study drug exposure will be also provided.

Treatment duration (in weeks) will be calculated as (the date of the last dose of IP - the date of first dose of IP +1)/7 and rounded to one decimal place. The specific definitions of the first and last dose dates are given below:

- First dose date: the date of the first dose of IP at Visit 2/ Week 0.
- Last dose date:
 - The date of last dose of IP captured at Visit 7/Week 48 or Early Termination Visit, whichever occurred first.
 - The date prior to Visit 7/Week 48, if the date of last dose of IP is unknown at Visit 7/Week 48
 - The date prior to Early Termination Visit, if the date of last dose of IP is unknown at Early Termination Visit
 - The last known study date if the subject is lost to follow-up

Imputation rules for partially or completely missing last dose date is specified in Appendix [A1 1](#).

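### For a subject who reached Week 48 with a completely missing last-dose date, SAP 10.1 and Appendix A1 1.4 give dates nominally 29 days apart, and the SAP does not say which governs

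*SAP*

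**What the plan says.** SAP 10.1 lists the last-dose date case by case. For a subject at Visit 7 whose date is not known, it takes: "The date prior to Visit 7/Week 48, if the date of last dose of IP is unknown at Visit 7/Week 48". The same section then adds: "Imputation rules for partially or completely missing last dose date is specified in Appendix" A1 1. It does not say whether the appendix replaces the list or only fills gaps in it.

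Appendix A1 1.4 has its own rule for the fully missing case: "When last dose date is completely missing, set last dose date to the minimum of (last known date in database, first non-missing Early Termination" visit date. The other term in that minimum is broad: "Last known date in database is defined as maximum of (last visit date, lab, vital signs, AE start or end dates", followed by concomitant medication and procedure dates, dosing dates and death date. Nothing limits it to the treatment period.

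Two facts about the design bear on this. Under Protocol 6.2.1, "An Early Termination Visit will be performed for subjects who are withdrawn from treatment for any reason". Under Protocol 3.3, an individual's study completion means "reaching Visit 7/48 weeks of treatment, and finishing the Observational Follow-up Visit at Week 52".

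**The concern.** A subject who finishes 48 weeks of treatment has no Early Termination visit. The appendix minimum then has only one term left, the last known date. For anyone who attends follow-up, that date is no earlier than the follow-up visit. SAP 5.3 places this visit in an observational period that begins the day after the treatment period ends, and the Protocol's Table of Events dispenses no drug at Visit 7. The appendix would therefore record dosing in a phase where the design has none, while 10.1 gives a plausible date for the same subject.

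Treatment duration is computed directly from the last-dose date. SAP 12 uses treatment duration as the exposure time, in the exposure-adjusted incidence rate (EAIR), of every subject without the event. An inflated duration lowers the rate. Two programmers following the two sections would not reproduce each other's exposure tables.

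**Working it through.** **Inputs.** First dose on Day 1. Visit 7 target Day 336 (SAP 5.5, safety window table). Follow-up at Week 52 (Protocol 3.3); SAP 5.3 says subjects "will be followed up for 28 days after the Visit 7/Week 48 or Early Termination visit". Visit windows of ±1 week (Protocol Table of Events), taken here to apply to the Week 52 visit as well. Duration in weeks = (last dose − first dose + 1) / 7 (SAP 10.1).

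**Reproducing the plan's day numbers.** 48 × 7 = 336, which matches the SAP table. 52 × 7 = 364 = 336 + 28, which matches the 28-day follow-up.

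**Completely missing date, nominal schedule.**
- SAP 10.1: last dose Day 336 − 1 = 335; duration 335 / 7 = 47.9 weeks.
- Appendix A1 1.4: no Early Termination date, so last dose is the last known date, Day 364 if follow-up is the latest record; duration 364 / 7 = 52.0 weeks.
- Difference: 364 − 335 = 29 days = 4.1 weeks; 29 / 335 = 8.7%.

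**Visit windows.**
- Follow-up exactly 28 days after the actual Visit 7: 29 days, whenever Visit 7 falls.
- Visit 7 on Day 336, follow-up a week early or late: 357 − 335 = 22 days, or 371 − 335 = 36 days.
- Each visit using its own window: 357 − 342 = 15 days (Visit 7 on Day 343), up to 371 − 328 = 43 days (Visit 7 on Day 329).
- An adverse-event, medication or procedure date after follow-up adds to these.
- No follow-up visit and no later record: the last known date is Visit 7 itself, a gap of 1 day.

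**Early terminators.** With a recorded Early Termination visit, 10.1 gives the day before it and the appendix gives the visit date: a 1-day gap.

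**Partial dates.** The appendix takes max[earliest possible date, min(latest possible date, last known date, Early Termination date)]. If the month is known, month end is a cap. For a last dose in the same 31-day month as Visit 7, with follow-up 28 days later, the excess over the day before Visit 7 is:
- Visit 7 on the 2nd: 30 − 1 = 29 days.
- Visit 7 on the 15th: 31 − 14 = 17 days.
- Visit 7 on the 31st: 31 − 30 = 1 day.

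If only the year is known, the cap is year end. The result is then the last known date whenever that falls in the same year, as for a fully missing date.

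**Pooled EAIR.** Suppose every subject completes without the event and a share f has the 29-day excess. The rate is multiplied by 335 / (335 + 29f):
- f = 5%: 335 / 336.45 = 0.996
- f = 10%: 335 / 337.9 = 0.991
- f = 20%: 335 / 340.8 = 0.983

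The documents do not give f; these shares are assumptions.

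**The case against.** The strongest defence is that 10.1 already governs. It has a study-specific rule for exactly this subject, and the appendix opens by calling its contents general conventions for reference, on which users may need to consult the study team. On that reading the specific rule prevails and nothing is overstated. This is the natural reading, and it is why the overstatement is conditional. It does not remove the conflict: 10.1 itself sends completely missing dates to the appendix, and 1.4 makes no exception for subjects who reached Week 48.

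It is also fair to say that few dates may be missing. Last dose is captured at Visit 7, drug accountability is scheduled there, and the appendix mentions a last-dose date on the treatment disposition page. Efficacy analyses use nominal visits and are untouched.

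Several stronger readings are tempting but not supported:
- A reader might infer that 4 weeks is a minimum. It is the nominal value. Windows allow 15 days, and Protocol 3.3 also defines completion for analysis as reaching Week 48, so a subject may have no later record at all.
- A reader might infer that all partial dates share the problem. Those with a known month are capped at month end.
- A reader might infer that the last known date can drift to the end of a month or year, because Appendix A1 1.2 says "Partially missing prior/concomitant medication stop dates will be imputed by the latest possible date given the non-missing field(s) of the date". That imputation is made in the medication analysis dataset, whereas 1.4 refers to dates in the database. Nothing says that one feeds the other.
- A reader might infer that adherence is misclassified. Every tablet taken to Day 335, scored against Day 364, gives (2 × 335 − 1) / (2 × 364 − 1) = 669 / 727 = 92.0%, still inside the 75% to 120% category. SAP 10.2 also uses the last dose date within the period, so Day 364 may not enter.
- A reader might infer a real shift in treatment-emergent events. The window would end 29 days later, but adverse events are recorded only to 28 days after the last dose. Beyond that, only serious events that become known to the investigator are added, so little would change.

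**Conclusion.** The two rules contradict each other for a subject who reached Week 48 with a completely missing last-dose date, and the SAP does not rank them. If Appendix A1 1.4 is programmed and a follow-up visit or other later date is on record, that subject's treatment duration is overstated by 29 days nominally (+8.7%), and the excess carries into the EAIR denominator. Year-only partial dates can behave the same way; month-known dates give a smaller excess. For early terminators with a recorded visit the rules differ by 1 day.

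The effect per affected subject is clear. The effect on pooled rates is small, under 2% even at an assumed 20% affected. This is a minor reproducibility defect in the safety exposure figures and no threat to the trial's conclusions.

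**What to change.** In Appendix A1 1.4, for subjects who reached Visit 7/Week 48, add the day before that visit as a further term in the minimum, for both completely missing and partial dates. Alternatively, state in 10.1 that its rules take precedence and the appendix applies only where they give no date. Leave the definition of the last known date unchanged. Stripping visit, adverse-event or medication dates from it would also alter the imputation for subjects lost to follow-up, where no conflict has been shown.

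The cost is one sentence in the SAP before database lock, with no change to data collection or conduct.
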